## 8.0 Eligibility Screening

8.1 *Describe screening procedures for determining subjects' eligibility. Screening refers to determining if prospective participants meet inclusion and exclusion criteria.*

*Include all relevant screening documents with your submission (e.g. screening protocol, script, questionnaire)*

Response: Potential participants may respond to flyers, posters, advertisements or word-of-mouth by phone call. First, they will be screened over the phone and if eligible, scheduled for a screening visit which may be the same day as the first study visit (Baseline Visit (if eligible)). A script will be used for the screening phone call plus a screening checklist. In the screening telephone conversation, women are asked if they are pregnant and are ineligible for the Screening Visit if they say yes. At the Screening visit, women of childbearing age are given a pregnancy test and if positive are ineligible. This testing is completed because of the possible need for Rescue Therapy if the study treatment is not successful. If the study treatment is not successful, the dentist/periodontist determines the nature and extent of the Rescue Therapy and it may include surgery and/or topical or systemic antibiotics. The risk to any fetus from the study treatment is very low. However, if topical or systemic antibiotics are required because of failure to respond to the study treatment, the risk to the fetus is higher. Hence, pregnancy tests will also be given at visits where additional therapy may be needed, and Arestin will NOT be given if the pregnancy test is positive. In addition, AxiUm, the patient data system in the School of Dental Medicine, will be accessed to identify patients with diabetes who might be eligible, willing and interested in joining the study. For these patients, we will obtain permission of [name] to contact identified patients, if he approves of the selection. Then an IRB-approved letter will be sent to the patients informing them of the study, telling them they may call us for more information or that we may call them to provide information about the study. Patients will also be told

they under no obligation to join the study. From there we will use the IRB-approved Telephone Screen Script and Screening Checklist to provide information to and assess eligibility of patient. All procedures thereafter will be the same as with other participants.

- N/A:** There is no screening as part of this protocol.

## 9.0 Recruitment Methods

- N/A:** This is a records review only, and subjects will not be recruited. NOTE: If you select this option, please make sure that all records review procedures and inclusion/exclusion screening are adequately described in other sections.

### 9.1 *Describe when, where, and how potential subjects will be recruited.*

*NOTE: Recruitment refers to how you are identifying potential participants and introducing them to the study. Include specific methods you will use (e.g. searching charts for specific ICD code numbers, Research Participant Groups, posted advertisements, etc.).*

**Response:** Participants will be recruited from previous studies (if they have indicated they are interested participating in other/new studies), as well as from responses to posters, flyers, advertisements, and word-of-mouth. All advertising materials that will be used will be submitted to the IRB for approval BEFORE they are used. In addition, we plan to contact senior citizens' centers asking them to hang study posters and inform their participants about the study.

Radio and television ads will be used for recruitment when other methods have declining effect/no longer work and resources allow. Final versions of ads (radio and/or TV) will be submitted to the IRB for approval before use.

The AxiUm system, the patient data system in the School of Dental Medicine, will be accessed to identify patients with diabetes who might be eligible, willing and interested in joining the study. After receiving a partial HIPAA waiver for this work, we will request permission from [name] to contact identified patients. If he approves, an IRB-approved letter will be sent to the patients informing them of the study, telling them they may call us for more information or that we may call them to provide information about the study. Patients will be told they under no obligation to join the study. We will use the IRB-approved Telephone Screen Script and Screening Checklist to provide information to and assess eligibility of patients. All procedures thereafter will be the same as with other participants.

### 9.2 *Describe how you will protect the privacy interests of prospective subjects during the recruitment process.*

*NOTE: Privacy refers to an individual's right to control access to him or herself.*

**Response:** Potential and enrolled participants will interact with the study staff, the dentists, registered dental hygienists, dental assistants, laboratory technicians, research associates and data manager, in an operatory in the PDRC. If participants chose NOT to interact with one of these people, we can accommodate the request to a limited degree by having another dentist, hygienist, dental assistant or laboratory technician “work” with them, but once seen/examined by a dentist or hygienist we need to keep the same examiner for consistency of clinical examination data. Participants can ask to be seen in an operatory with a door that can be closed to better ensure privacy. Participants may also choose not to answer questions, but if those questions provide critical information needed to answer the research questions, the person will not be allowed to remain in the study. When participants have samples such as saliva collected, they are provided privacy from the view of others; blood is collected and height and weight measured out of the view of others as well.

The PDRC is a suite of rooms and operatories some of which have doors for privacy and quiet. However, even operatories without doors have limited access and view and so provide a good degree of privacy to everyone.

Participants “self-select” to join the study by calling us in response to flyers, posters and ads. They are told they may withdraw from the study at any time with no adverse effects on them. They are told we need certain data and that data need is explained prior to enrollment (at the time of the screening call and during the screening visit/first study visit.

### 9.3 Identify any materials that will be used to recruit subjects.

*NOTE: Examples include scripts for telephone calls, in person announcements / presentations, email invitations.*

 For advertisements, include the final copy of printed advertisements with your submission. When advertisements are taped for broadcast, attach the final audio/video tape. NOTE: You may submit the wording of the advertisement prior to taping to ensure there will be no IRB-required revisions, provided the IRB also reviews and approves the final version.

**Response:** Posters, flyers, ads and word-of-mouth, and AxiUm; a script is used for responses to these methods. All advertising materials that will be used will be submitted to the IRB for approval BEFORE they are used.

## 10.0 Procedures Involved

**10.1** *Provide a description of all research procedures or activities being performed and when they are performed once a subject is screened and determined to be eligible. Provide as much detail as possible.*

*NOTE: This should serve as a blueprint for your study and include enough detail so that another investigator could pick up your protocol and replicate the research. For studies that have multiple or complex visits or procedures, consider the addition of a schedule of events table in in your response.*

**Response: SCREENING VISIT:**

**Subject will be recruited by advertisements, word-of-mouth, and by flyer and posters hung around the University and local community.**

- 1. Consent:** Visits will take place in the Periodontal Disease Research Center, [name], UB South Campus. We will explain the study and study procedures to participants. If they agree to participate in the study, we will ask them to read and sign the consent form.
- 2. Demographic:** Medical and dental histories and subject demographic information include date of birth, gender, racial and ethnic background, medical and dental histories, medications, lifestyle habits, dental home care, smoking status will be obtained. Height, weight, and blood pressure will be measured.
- 3. Oral health examination for eligibility:** The oral health examination including measurements to assess teeth and gingival status will be completed. Dental radiographs will be taken unless suitable x-rays taken elsewhere within the past two years can be acquired. (Women of childbearing age will be required to take a pregnancy test before any radiographs are taken.)
- 4. Instruct in how to collect fecal samples at home, and give a fecal collection kit. Instruct to refrain from showering or washing hair for 24 hours before study visit.**
- 5. Make an appointment for Baseline visit.**

**BASELINE VISIT:**

- 1. Review medical and dental histories.**
- 2. Baseline Taste Test**
- 3. Oral Health Examination:**
  - a) Plaque Index (PI)**
  - b) Probing Pocket Depth (PPD)**
  - c) Bleeding on Probing (BOP)**
  - d) Gingival Index (GI)**
  - e) Clinical Attachment Level (CAL)**
- 4. Collect samples:**
  - a) Blood (FBS, HbA1c, Insulin, hs-CRP and microbiome testing, and for future testing of C-peptide, proinsulin, total GLP-1, PYY,**

DPP-IV, glucagon, LPS, soluble-TNF $\alpha$  RI and RII, MGO, TMAO, creatinine, and for future unknown testing.

- b) Subgingival plaque and saliva.
- c) Fecal, skin, and vaginal samples

3. Treatment: All participants will receive full mouth SRP within one month of the baseline visit.

4. Oral health instruction: All participants will receive oral hygiene instruction from the hygienist.

5. Participants will be randomized into one of the four groups.

6. Groups A and B will receive the product, Soft-Picks, and information on how to use them.

7. Make an appointment for 3 months after Baseline Visit.

#### 3-MONTH VISIT:

1. Collect the unused Soft-Picks and Paroex® bottle from the participants in the Groups A and B.

2. Ask the subjects to answer the Adverse Event, Taste and Compliance questionnaire.

3. Review medical and dental histories.

4. Taste Test.

5. Oral health examination

6. Collect saliva, subgingival plaque and stool/fecal samples.

6. Anterior teeth cleaning: All subjects will receive anterior teeth cleaning.

7. Groups A and B will have the product, Soft-Picks, replenished and usage instructions reviewed as needed.

8. Make or confirm the next appointment.

9. If any sites where pocket depths stay the same and are  $\geq 5$  mm or if the pockets deepen, periodontal treatment will be repeated.

Exact treatment will be determined by the clinician (dentist or periodontist). The treatment will be explained to the participant and questions will be answered beforehand. Options for Rescue Therapy treatment are:

- Option 1: No additional treatment.
- Option 2: Pocket depths of  $\geq 5$  mm will receive scaling and root planing,
- Option 3: Pocket depths of  $\geq 5$  mm will receive scaling and root planing with the addition of a local antimicrobial agent,

- **Option 4:** Pocket depths of  $\geq 5$  mm will receive modified Widman flap surgery,
- **Option 5:** Pocket depths of  $\geq 5$  mm will receive modified Widman flap surgery with the addition of the GUIDOR® *easy-graft®* CLASSIC Alloplastic Bone Grafting System to infrabony defects that are amenable to regeneration.

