**Response:**

1. Supportive Periodontal Therapy (SPT) using Paroex® mouthrinse (0.12% chlorhexidine) and Soft-Picks leads to improved clinical status and change in oral microbiome greater than when Scaling and Root Planing (SRP) only is used.

2. There will be about 35% who will be “Poor Responders” (PRs) (those needing Rescue Therapy). The number of PRs in diabetics will be higher than in non-diabetics. Poor Responders will have different clinical and microbiome in characteristics than responders.

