#### **6-MONTH VISIT:**

1. Collect the unused Soft-Picks from the subjects in the Test Group.
2. Ask the subjects to answer the Adverse Event, Taste and Compliance questionnaire.
3. Review medical and dental histories.
4. Taste Test.
5. Oral health examination
6. Collect samples: blood (FBS, HbA1c, Insulin, hs-CRP and microbiome testing, and for future testing of C-peptide, proinsulin, total GLP-1, PYY, DPP-IV, glucagon, LPS, soluble-TNF $\alpha$  RI and RII, MGO, TMAO, creatinine, and for future unknown testing), subgingival plaque, saliva, fecal, skin, and vaginal samples.
7. Retreat all PD  $\geq 5$  mm sites. Subjects will receive additional treatment (Rescue Therapy), including surgery and/or topical or systemic antibiotics, if a clinician (dentist or periodontist) decides they need it. Rescue Therapy is standard of care for non-responsive periodontal lesions, the type depending on the clinical status of the participant. The need for Rescue Therapy (yes, no and type) will be noted in the study records and considered in the analysis of the study data. If on examination, a participant presents with an area showing a clinically defined worsening of their periodontal condition, rescue therapy will be initiated. This therapy will reduce the chance of the tooth being lost from periodontal disease. Rescue therapy will be provided to sites that remain at  $\geq 5$  mm or those demonstrating an increase in pocket depths of  $\geq 2$  mm from the baseline visit bringing them to or above the 5 mm level. Treatment will consist of scaling and root planing of the affected tooth and if the pocket depth is  $\geq 5$  mm, the site may also be treated by local drug delivery with Arestin. In women of childbearing potential, a urine pregnancy test will be provided prior to the placement of Arestin. If the pregnancy test is positive, Arestin will not be used in treatment. Local anesthetic may be used during the procedure as needed. Other treatments for saving the tooth may be given as deemed necessary by the dentist/periodontist clinician, as described above (Number 9 of the 3-

**month Visit).** The clinician will discuss the additional treatment with the participant before it is provided. The clinician providing the rescue therapy in a given subject should not be the clinician that will provide the periodontal measurements for that participant during the study.

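### The retreatment rules at months 3, 6 and 9 contradict each other and themselves, so Poor Responder status in Hypothesis 2 depends on which visit's rule is applied

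*Combined protocol and SAP*

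**What the plan says.** **Month 3 (section 10.1, 3-Month Visit, item 9).** The trigger is a site whose depth is unchanged and at least 5 mm, "or if the pockets deepen, periodontal treatment will be repeated". The item then says "Exact treatment will be determined by the clinician (dentist or periodontist") and lists five Rescue Therapy choices. The first is "Option 1: No additional treatment". Options 2 to 5 are each written for pockets of at least 5 mm; Option 3, for example, reads "mm will receive scaling and root planing with the addition of a local antimicrobial agent".

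**Month 6 (item 7) and month 9 (item 6).** Both open with "Retreat all PD" of at least 5 mm. Both also provide rescue to sites that remain at 5 mm or more, or that have increased by at least 2 mm "from the baseline visit bringing them to or above the 5 mm level". Month 6 adds that a worsening judged clinically starts rescue, without a millimetre value.

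**Where the rules are used.** The primary endpoint (section 2.1) is the 6-month change in PPD. Hypothesis 2 (section 1.2) says "There will be about 35% who will be" Poor Responders, defines them as participants who need Rescue Therapy, and predicts more of them among participants with diabetes. The visit instructions say that rescue will be recorded and taken into account in the analysis. Section 17.1 gives no method for this.

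**The concern.** The rule that decides who is retreated has two roles here. It is a treatment decision that can change pocket depth, and at month 3 that decision comes before the primary endpoint. It also supplies the outcome in Hypothesis 2. If the same pair of readings counts as needing rescue at one visit and not at another, the Poor Responder proportion has no single meaning. It cannot be compared across visits or set against the expected 35%, and the comparison of diabetic with non-diabetic participants inherits the ambiguity.

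The deepening part of the month-3 trigger also has no minimum change, so a 1 mm difference between two readings could meet it.

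**Working it through.** No figure in the plan can be reproduced on this point: the 35% is stated without a derivation, and the sample size does not depend on these rules. The check applies each sentence to the same readings.

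**Inputs.** The four conditions come from section 10.1. Three assumptions are mine: readings in whole millimetres, baseline as the reference visit at month 3, and remaining at 5 mm or more read as at least 5 mm both at baseline and at the visit.

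- Month-3 trigger: (visit = baseline and visit ≥ 5) or visit > baseline.
- Month-3 active treatment (Options 2 to 5): trigger met and visit ≥ 5.
- Months 6/9, retreat-all sentence: visit ≥ 5.
- Months 6/9, rescue sentence: (baseline ≥ 5 and visit ≥ 5) or (visit − baseline ≥ 2 and visit ≥ 5).

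Baseline depths 2 to 7 mm crossed with visit depths 2 to 7 mm give 6 × 6 = 36 pairs. The month-3 trigger and the two month-6/9 sentences disagree on 3 + 1 + 3 = 7 of them:

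| Baseline to visit (mm) | Month-3 trigger | Month-3 active option | Months 6/9, retreat all | Months 6/9, rescue sentence |
|---|---|---|---|---|
| 2 to 3, 2 to 4, 3 to 4 | yes | none | no | no |
| 4 to 5 | yes | yes | yes | no |
| 6 to 5, 7 to 5, 7 to 6 | no | not reached | yes | yes |

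The 8 to 6 mm case lies outside the grid but follows the last row. It is neither unchanged nor deeper, so it triggers nothing at month 3; it was and is at least 5 mm, so both month-6/9 sentences cover it.

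**Effect of alternative readings.**

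1. Suppose the deepening part of the month-3 trigger refers only to pockets now at 5 mm or more. The first row then drops out and four pairs still disagree.
2. Suppose also that the two month-6/9 sentences are cumulative. The 4 to 5 mm pair then agrees and three pairs remain (6 to 5, 7 to 5, 7 to 6). On this reading the 2 mm condition does nothing, because every site it describes is already covered by the retreat-all sentence.
3. Suppose instead that retreatment and rescue are different things at months 6 and 9. A 4 to 5 mm site is then retreated without counting as rescue, whereas month 3 lists scaling and root planing as a Rescue Therapy option.

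**Consequence for Hypothesis 2.** Take a participant whose deep sites have all improved but remain at 5 mm or more, with no other site deeper. By the month-3 trigger this participant does not need rescue. By the month-6 or month-9 rule, the same chart does.

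**Consequence for the primary endpoint.** At month 6 the examination (item 5) is listed before retreatment (item 7). Only month-3 treatment can therefore reach the 6-month PPD value, and the options there run from nothing to flap surgery with bone graft.

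**The case against.** Several stronger readings are tempting, and the documents do not support them.

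- **That months 6 and 9 act only on a 2 mm rise.** They do not. Both also cover every site at 5 mm or more, and month 6 has the further clause on clinical worsening. That clause also means a 2 to 3 mm reading is not fully settled at month 6.
- **That probing error would send many participants into retreatment at month 3.** A trigger is not a treatment. The clinician chooses, no treatment is allowed, and no active option names a site below 5 mm. A 4 to 5 mm misreading would be retreated at months 6 and 9 as well. The protocol describes calibration to a gold standard (section 14.4) and keeping the same examiner (section 9.2), but gives no repeatability figure. Any rate would rest on assumed error, site count and correlation between sites, and would ignore healing after scaling and root planing.
- **That the month-3 trigger shows the expected 35% to be wrong.** Hypothesis 2 concerns participants who need rescue, recorded after a clinician's decision. It does not concern those with at least one site past a reading threshold.
- **That all visits must share one trigger.** Nothing in the protocol says so, and staged rules could be deliberate.

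It is also fair to say that the deepening part may refer only to deep pockets, and that the month-6/9 sentences may be cumulative. Both are possible, but the text does not settle either. Even with both granted, improved sites still at 5 mm or more are handled differently by visit, and the month-3 item still says both that treatment will be repeated and that it need not be.

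**Conclusion.** The concern holds as a contradiction between stated rules. Of 36 whole-millimetre pairs examined, seven are handled inconsistently on the literal wording, and three remain so on the most accommodating reading of those sentences. These are counts of possible readings, not of sites or participants, and they rest on the three assumptions listed with the check.

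The clearest divergence is that improved sites still at 5 mm or more are covered at months 6 and 9 but do not themselves trigger anything at month 3. The month-3 item also conflicts with its own options list. Poor Responder status, and hence the 35% and the diabetic versus non-diabetic comparison, therefore depends on which visit's rule is used.

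A 1 mm reading difference could meet the month-3 trigger before the primary endpoint. How often it would, and what it would do to 6-month PPD, cannot be stated from these documents.

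**What to change.** 1. **Protocol wording.** The investigators should reconcile item 9 of the 3-Month Visit, item 7 of the 6-Month Visit and item 6 of the 9-Month Visit with each other and with the list of options. Which rule is right is theirs to decide. Any intended difference between visits should be stated as intended.
2. **Hypothesis 2 analysis.** Define Poor Responder by one prespecified definition applied to the PPD charted at each visit. Report it alongside the rescue actually given. State to which definition and visit the expected 35% refers.

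A common definition makes the classification comparable across visits, but it cannot undo treatment already given at month 3. How 6-month PPD is analysed after month-3 retreatment still has to be stated separately.

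**Cost.** A wording amendment and a little extra analysis. No new data are needed, since PPD change is already an endpoint at months 3, 6, 9 and 12; this assumes that depths are stored by site.

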#### **6-MONTH VISIT:**

1. Collect the unused Soft-Picks from the subjects in the Test Group.
2. Ask the subjects to answer the Adverse Event, Taste and Compliance questionnaire.
3. Review medical and dental histories.
4. Taste Test.
5. Oral health examination
6. Collect samples: blood (FBS, HbA1c, Insulin, hs-CRP and microbiome testing, and for future testing of C-peptide, proinsulin, total GLP-1, PYY, DPP-IV, glucagon, LPS, soluble-TNF $\alpha$  RI and RII, MGO, TMAO, creatinine, and for future unknown testing), subgingival plaque, saliva, fecal, skin, and vaginal samples.
7. Retreat all PD  $\geq 5$  mm sites. Subjects will receive additional treatment (Rescue Therapy), including surgery and/or topical or systemic antibiotics, if a clinician (dentist or periodontist) decides they need it. Rescue Therapy is standard of care for non-responsive periodontal lesions, the type depending on the clinical status of the participant. The need for Rescue Therapy (yes, no and type) will be noted in the study records and considered in the analysis of the study data. If on examination, a participant presents with an area showing a clinically defined worsening of their periodontal condition, rescue therapy will be initiated. This therapy will reduce the chance of the tooth being lost from periodontal disease. Rescue therapy will be provided to sites that remain at  $\geq 5$  mm or those demonstrating an increase in pocket depths of  $\geq 2$  mm from the baseline visit bringing them to or above the 5 mm level. Treatment will consist of scaling and root planing of the affected tooth and if the pocket depth is  $\geq 5$  mm, the site may also be treated by local drug delivery with Arestin. In women of childbearing potential, a urine pregnancy test will be provided prior to the placement of Arestin. If the pregnancy test is positive, Arestin will not be used in treatment. Local anesthetic may be used during the procedure as needed. Other treatments for saving the tooth may be given as deemed necessary by the dentist/periodontist clinician, as described above (Number 9 of the 3-

**month Visit).** The clinician will discuss the additional treatment with the participant before it is provided. The clinician providing the rescue therapy in a given subject should not be the clinician that will provide the periodontal measurements for that participant during the study.

**8.** Groups A and B will have the product, Soft-Picks, replenished and usage instructions reviewed as needed.

**9.** Confirm the next appointment.

